3.11. Listings

To review the snapshot clinical data for a patient, in case a safety event occurred, additional patient summary listings will be performed. For the following categories listings may be presented: demographics, medical history, history of primary breast cancer, surgery, physical examination, vital signs, radiological examinations, hematology, chemistry, electrolytes, DLCO, GDC-0032/placebo administration, letrozole administration, concomitant medication, treatment completion and surgery at treatment completion.

3.12. Covariates

To adjust for the possible effect of demographic or prognostic factors multivariate analyses will be performed. To avoid multi-collinearity between the covariates, prior correlation analyses will be performed. Depending on the statistical results and the clinical relevance, highly correlated covariates may be excluded from multivariate analyses. Binary dependent variables will be analyzed using logistic regression models. Metric dependent variables will be analyzed using general linear models or a non-parametric equivalent if appropriate. Forest plots will be given where appropriate.

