2.2.2. Study duration – end of study

The end of study (EOS) is defined as the date when the last patient has her post-surgery visit. The total duration of the study is expected to be approximately 24 months for enrollment, plus 5.5 months after last patient in.

2.3. **Randomization and stratification criteria**

After written informed consent form (ICF) has been obtained and eligibility has been established, the study site will obtain a patient's identification number and treatment assignment using a permuted block randomization algorithm via an interactive voice or web-based response system (IxRS).

Patients will be randomized into one of the two treatment arms in a 1:1 ratio based on the following stratification factors:

- Tumor Size (T1-T2 vs. T3)
- Nodal Status (cytologically positive vs. radiologically or cytologically negative). If on ultrasound examination there is evidence of suspicious axillary lymph nodes at the baseline examination, then FNA or core biopsy is required to confirm nodal status.

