2.4. Number of subjects - sample size estimation

This study is designed for testing the effect of GDC-0032 on the two co-primary endpoints in all enrolled patients and in the PIK3CA MT patients and plans to enroll 330 patients in total. Assuming the PIK3CA mutation status will not be available (unknown) for approximately 10% of the patients and the prevalence of PIK3CA MT is 40%, there will be approximately 120 patients in the PIK3CA MT cohort.

Given that the PIK3CA mutation status is not a stratification factor for randomization, there might be a possible imbalance between treatment arms within the PIK3CA MT cohort, which may reduce the statistical power in this cohort. To ensure the study provides sufficient statistical power even when the treatment assignment is imbalanced, the sample size was calculated based on a conservative scenario by assuming that the treatment assignment imbalance in PIK3CA MT is 40% vs. 60%. The sample size was calculated based on a χ^2 -test using continuity correction (Ury and Fleiss 1980).

To control an overall, two-sided, family-wise error rate under 20% for each analysis population, we use a two-sided significance level of 16% and 4% for the co-primary endpoints MRI ORR, and pCR, respectively.

Assuming 10% of the patients are unevaluable for the MRI ORR, approximately 300 enrolled patients and 108 patients in the PIK3CA MT cohort will be evaluable for analyses. This sample size allows us to detect an absolute percentage increase of 24% in MRI ORR rate in the letrozole plus GDC-0032 arm (64%) versus the letrozole plus placebo arm (40%; Smith et al. 2005; Ellis and Ma 2007) in the PIK3CA MT cohort at 80% power and 16% two-sided significance level. The minimal detectable difference for ORR is approximately 15%.

Assuming that all patients are evaluable for pCR (i.e., approximately 330 enrolled patients and 120 in the PIK3CA MT cohort), this sample size provides 80% power to detect an absolute percentage increase of 18% in pCR in the letrozole plus GDC-0032 arm (19%) versus the letrozole-only arm (1%, Smith et al. 2005; Ellis and Ma 2007) in the PIK3CA MT cohort at the 4% two-sided significance level. The minimal detectable difference for pCR rate is approximately 13%.

The study is considered positive if at least one population shows a statistically significant result regarding the co-primary endpoints.

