3.10.2. Analysis for exploratory endpoints

Comparisons between treatment arms in ORR (grouped as responder vs. non-responder), pCR rate and PEPI score according to the decrease in Ki67 will be analyzed using appropriate regression analysis models (depending on the distribution of the variables), e.g. logistic regression models, adjusting for tumor size and nodal status in all randomized population and in PIK3CA MT population. Concordance will be examined by frequencies and percentages. Rates will be summarized descriptively.

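### Logistic regression is planned for pCR without a sparse-data method, although at the SAP's own 1% control rate the PIK3CA MT cohort has no control responder, and so no finite odds ratio, in about half of trials or more

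*SAP*

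**What the plan says.** Section 3.12 of the SAP plans multivariate analyses to adjust for demographic and prognostic factors, with forest plots where suitable. On the model it says "Binary dependent variables will be analyzed using logistic regression models". The sentence after it gives continuous outcomes an alternative: "Metric dependent variables will be analyzed using general linear models or a non-parametric equivalent if appropriate". Binary outcomes get none.

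Section 3.10.2 covers pCR, ORR and PEPI score in relation to the early fall in Ki67. It asks for a regression model suited to the variable, "e.g. logistic regression models, adjusting for tumor size and nodal status in all randomized population and in PIK3CA MT population".

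Section 2.4 sizes the MT cohort for an "absolute percentage increase of 18% in pCR in the letrozole plus GDC-0032 arm (19%) versus the letrozole-only arm", the latter assumed to be 1%. The numbers are "approximately 330 enrolled patients and 120 in the PIK3CA MT cohort".

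Two places deal with data that do not suit the planned method. Section 3.1.5 replaces the CMH test by Fisher's exact test when cells are sparse. Section 3.1.1, under outliers, says in general terms that an analysis will be changed if the data structure does not permit it, but names no method.

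**The concern.** A 1% control rate in an MT control group of 48 to 72 patients means an expected 0.5 to 0.7 control responders, so an empty control cell is an ordinary outcome. When it occurs and the active arm has both responders and non-responders, the logistic likelihood keeps rising as the treatment coefficient grows. No finite odds ratio exists, and the standard error from the last iteration has no meaning.

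At stake is the purpose of section 3.12: to show whether the pCR effect holds after adjustment. The adjusted odds ratio and the usual forest-plot interval would be unusable in the cohort the trial was sized for. The replacement method would then be chosen after separation had been seen, possibly after unblinding. The SAP foresaw sparse cells for the CMH test but did not carry that care over to the regressions.

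**Working it through.** **Inputs from the SAP.** pCR 1% control and 19% active; 120 MT patients; two-sided 4% for the co-primary pCR test; 80% power; continuity-corrected chi-square (all section 2.4). Allocation: "Patients will be randomized into one of the two treatment arms in a 1:1 ratio" (section 2.3), so about 60/60 in MT. The sizing allows for imbalance, "assuming that the treatment assignment imbalance in PIK3CA MT is 40% vs. 60" per cent, so 48/72 or 72/48. All other tests are at 5% (section 3.4).

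**Reproducing the plan's figure.** Take control n, active kn, k = 1.5, d = 0.18.
- Pooled rate = (0.01 + 1.5 × 0.19)/2.5 = 0.118.
- Uncorrected n = [2.054 × √(0.118 × 0.882 × (1 + 1/1.5)) + 0.842 × √(0.01 × 0.99 + 0.19 × 0.81/1.5)]² / 0.18² ≈ 40.
- Corrected n = (n/4) × [1 + √(1 + 2(1 + 1/k)/(n d))]² ≈ 49.
- Total = 49 × 2.5 = 122.5, against 120 stated. Corrected power at 48/72 is 79.1%, against 80% stated.

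The 1% and 19% rates are therefore the ones the design rests on.

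**Probability of an empty control cell.** P(no control pCR) = 0.99^n.
- 48 controls: 61.7%
- 60 controls: 54.7%
- 72 controls: 48.5%
- 165 controls (330/2, all randomized): 19.0%

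The probability of no responder in the active MT arm at 19% is below 0.005%, so an empty control cell almost always means an infinite odds ratio.

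**Sensitivity to the control rate, 60 controls.** 74% at 0.5%, 40% at 1.5%, 30% at 2%, 16% at 3%.

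**Expected MT events.** 60/60: 0.6 + 11.4 = 12.0. 48/72: 0.48 + 13.68 = 14.2. 72/48: 0.72 + 9.12 = 9.8.

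**Simulation.** 3,000 trials per allocation; logistic model with arm, tumor size and nodal status; two-sided 5%. Assumptions not in the SAP: T3 in 20%, node-positive in 35%, neither prognostic for pCR. The Firth column uses the first 600 trials of each row.

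| Control/active | Empty control cell | Wald | Likelihood ratio | Firth | Fisher |
|---|---|---|---|---|---|
| 60/60 | 55% | 40% | 98% | 96% | 93% |
| 48/72 | 62% | 30% | 98% | 96% | 96% |
| 72/48 | 49% | 46% | 97% | 95% | 95% |
| 165/165 | 18% | 82% | 100% | 100% | 100% |

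In the MT trials with an empty control cell, the Wald p was never below 0.96 (fit stopped at 15 iterations), while Fisher's test was significant in 98% to 99% of them.

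**One data set, 0/60 against 11/60, arm only.** Fisher p = 0.0006. Likelihood ratio: 2 × (−28.585 + 36.765) = 16.36 on 1 df, p = 0.00005. The Wald p is 0.55 after 8 iterations, 0.78 after 10 and 0.97 after 15, so it records only where the algorithm stopped.

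**The case against.** The case against is substantial, and most of it limits the point without removing it.

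- **The co-primary result.** A reader might infer that the pCR conclusion is at risk. It is not: section 3.6.2 uses the CMH test, and section 3.1.5 provides Fisher's test for sparse cells.
- **A p-value near 1.** A reader might infer that the plan yields a non-significant result when the drug works. The SAP names no Wald test. A likelihood-ratio test from the same model keeps 97% to 98% power in MT. Still, the infinite estimate remains, and the Wald interval is the usual forest-plot output.
- **No fallback.** Section 3.1.1 does give a general permission to change the analysis. It fixes no method in advance, and that narrower criticism stands.
- **Logistic regression is not mandatory in 3.10.2.** Correct: it is an example there. The analysis concerns pCR by fall in Ki67, and section 3.10.1 takes it to MT only after significance in all randomized patients. The simulation contains no Ki67 term, so it does not reproduce that model. Section 3.12 has neither limit, but it names neither pCR nor the MT cohort; the link is that pCR is a binary co-primary endpoint.
- **Estimator.** Section 3.12 does not specify one, and Firth regression is a form of logistic regression. The proposed change therefore fits the text, which supports writing it in.
- **Other pCR definitions.** Section 3.7.2 compares ypT0 ypN0 and breast pCR by CMH, so they are outside this point.

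**Conclusion.** The point holds in limited form. At the SAP's own planning rates, maximum-likelihood logistic regression for pCR gives no finite treatment odds ratio in about 49% to 62% of MT cohorts and in about 19% of trials for all randomized patients. The plan names no method for that case.

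These shares rest on the 1% control rate; with 60 MT controls the share falls to 30% if the true rate is 2%. The infinite estimate does not depend on the choice of test. The low Wald power (30% to 46% in MT) does, and it also rests on the assumed covariate shares. No confirmatory conclusion changes. The weakness lies in the adjusted and exploratory pCR analyses and is worth correcting because the remedy is cheap.

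**What to change.** In sections 3.12 and 3.10.2, state that regression models for total pCR use Firth penalised-likelihood logistic regression, with profile penalised-likelihood confidence intervals and tests at the two-sided 5% level of section 3.4. Make arm, tumor size and nodal status the base model, and keep further covariates few, because only about 10 to 14 MT events are expected. Ordinary logistic regression can stay for ORR, where the assumed rates of 40% and 64% raise no such problem.

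Firth is preferred to the likelihood-ratio test alone because it also supplies an estimate; it was finite in every simulated trial. Its power in MT (95% to 96%) was close to that of the likelihood-ratio test (97% to 98%). The cost is a short addition to each of the two sections, one model option in the program, and slight shrinkage of the estimates.

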3.13. Software

Analyses will be done by members of the biostatistics group at ABCSCG using statistical analysis system (SAS) software (SAS® version 9.3 or higher). If necessary, selected other software will be used.

4. Changes of analysis compared to study protocol

Abbreviation of progesterone receptor changed to PgR as PR is used for partial response.

The following exploratory objective was included to be consistent with the outcome measures given in the protocol: 'ORR, pCR rate, and PEPI scores according to the decrease in Ki67 after 2 weeks of letrozole plus GDC-0032 and letrozole plus placebo.'

5. Addendum to the statistical analysis plan

The Addendum to the SAP lists additional analyses for secondary endpoints calculated after finalization of the SAP (V2), including a description of and a rationale for these additions.

As addition to the main results for the two secondary efficacy endpoint measures in PIK3CA WT population, bar charts for rates (%) by treatment arm were given.

Also for further secondary endpoint measures several figures were created:

- Bar charts for rates (%) of locally assessed ORR by alternative methods were given by treatment arm for all three patient populations;
- for change in Ki67 boxplots either by treatment arm or by mutation status grouped by time point, individual patients plots for each treatment arm and either with/without ORR or mutation/wild type by with/without ORR as well as bar charts for proportional

change by treatment arm grouped by time difference (BL-W3, BL-SU, W3-SU) for all three patient populations were shown;

- Bar charts for frequency (%) of PEPI score as well as PEPI score risk groups by treatment arm for relapse-free/breast cancer-specific survival were created;
- Bar charts for change in enhancing tumor volume by treatment arm grouped by mutation status for absolute/percentage change were presented.

Additionally, because of the unexpected results with regard to the changes in Ki67 and the PEPI score, frequencies and percentages of time from EOT to surgery for GDC, Letrozole and overall were calculated.

6. References

	RECIST v1.1	Modified RECIST Early Breast Cancer Neoadjuvant Therapy
Modalities	CT as primary modality, ultrasound not recommended	No CT; primary assessments by MRI; also assessments by ultrasound, mammography, and clinical exam
Lymph nodes	May be considered target lesions based on size criteria (≥ 15 mm in SAD)	Only axillary lymph nodes assessed; nodes that are considered abnormal on imaging (based on morphological factors including, but not limited to SAD) to be followed as non-target lesions
Possibility of having only non-target disease	Allowed	Not allowed; primary breast lesions must be measurable by MRI

CT = computed tomography; MRI = magnetic resonance imaging; SAD = short axis dimension.

BASELINE DOCUMENTATION OF TARGET AND NON-TARGET LESIONS

To assess objective response or future progression, it is necessary to estimate the overall tumor burden at baseline and to use this as a comparator for subsequent measurements. All baseline evaluations should be performed as close as possible to the treatment start and never more than 4 weeks before the beginning of the treatment.

Method of Measurement

According to RECIST 1.1 guidelines, MRI is the preferred modality to follow breast lesions in a neoadjuvant setting. CT is currently the preferred modality for assessing metastatic disease, but should not be used in this focused setting of neoadjuvant therapy in early breast

¹ Eisenhauer EA, Therasse P, Bogaerts J, et al. New response evaluation criteria in solid tumors: Revised RECIST guideline (Version 1.1). Eur J Cancer 2009;45:228–47.

cancer. Ultrasound, mammography, and clinical exam are all common and useful modalities for assessing breast lesions, and will also be used to assess response in this protocol, adhering to response criteria as presented in this appendix.

Target Lesions

Target lesions should be selected on the basis of their size (lesions with the longest diameter) and should lend themselves to reproducible repeated measurements. Up to 2 lesions in the breast may be identified as target lesions. A sum of the diameters of all target lesions will be calculated and reported as the baseline sum of diameters. The baseline sum of diameters will be used as a reference to further characterize any objective tumor regression in the measurable dimension of the disease. Lesions that meet the criteria for radiographically defined simple cysts should not be considered malignant lesions (neither target nor non-target) since they are, by definition, simple cysts. Pathologic axillary lymph nodes are not to be designated as target lesions, and lymph node measurements are not to be included in the sum of diameters (see below for more detail).

Bilateral breast imaging studies should be conducted at each study assessment. The same method of measurement and the same technique should be used to characterize each target lesion at baseline and during the study, and all measurements should be recorded in metric notation. Care must be taken in measurement of target lesions with different modalities, since the same lesion may appear to have a different size with each modality. If for some reason the same imaging modality cannot be used at a scheduled assessment time point, then the case should be discussed with the radiologist to determine if substitution of any other approach is possible and, if not, the patient should be considered not evaluable at that time point, for that particular type of imaging assessment.

Non-Target Lesions

Non-target lesions may include any other measurable breast lesions not identified as target lesions, as well as truly non-measurable lesions, such as diffuse skin thickening or other lesions not measurable by reproducible imaging techniques.

Lymph nodes merit special mention since they are normal anatomical structures that may be visible by imaging even if not involved by tumor. Axillary lymph nodes are known to vary widely in size, and signs of abnormality in axillary lymph nodes on imaging include other morphological findings often in addition to changes in nodal size. For these reasons, pathologic axillary lymph nodes on imaging should be identified as non-target lesions at baseline. Change in short-axis dimension may be considered in the assessment of pathology, but measurements are not required, and these lesions should be followed qualitatively, as described below at each response assessment time point.

Signs of lymph node pathology on imaging include the following:

- Increase in short axis dimension
- Thickened cortex, either diffusely or asymmetrically enlarged
- Thinning, or replaced fatty hilum
- Irregular margins or spiculations

- Rim enhancement
- Decreased echogenicity of cortex
- Perinodal edema

EVALUATION OF RESPONSE

Evaluation of Target Lesions

This section provides the definitions of the criteria used to determine objective tumor response for target breast lesions:

- Complete response (CR): disappearance of all target lesions
- Partial response (PR): at least a 30% decrease in the sum of diameters of target lesions, taking as reference the baseline sum of diameters
- Progressive disease (PD): at least a 20% increase in the sum of diameters of target lesions, taking as reference the smallest sum on study (nadir), including baseline

In addition to the relative increase of 20%, the sum must also demonstrate an absolute increase of at least 5 mm.

The appearance of one or more new lesions is also considered progression.

- Stable disease (SD): neither sufficient shrinkage to qualify for PR nor sufficient increase to qualify for PD, taking as reference the smallest sum on study

Special Notes on the Assessment of Target Lesions

Target Lesions That Become Too Small to Measure. While on study, all lesions recorded at baseline should have their actual measurements recorded at each subsequent evaluation, even when very small (e.g., 2 mm). However, sometimes lesions that are recorded as target lesions at baseline become so faint on imaging that the radiologist may not feel comfortable assigning an exact measure and may report them as being too small to measure. When this occurs, it is important that a value be recorded on the CRF as follows:

- If it is the opinion of the radiologist that the lesion has likely disappeared, the measurement should be recorded as 0 mm.
- If the lesion is believed to be present and is faintly seen but too small to accurately measure, BML (below measurable limit) should be indicated.

To reiterate, however, if the radiologist is able to provide an actual measure, that should be recorded, and, in that case, BML should not be ticked.

Lesions That Split or Coalesce on Treatment. When non-nodal lesions fragment, the longest diameters of the fragmented portions should be added together to calculate the target lesion sum. Similarly, as lesions coalesce, a plane between them may be maintained that would aid in obtaining maximal diameter measurements of each individual lesion. If the lesions have truly coalesced such that they are no longer separable, the vector of the longest diameter for the coalesced lesion should be recorded.

Evaluation of Non-Target Lesions

This section provides the definitions of the criteria used to determine the tumor response for any non-target lesions identified at baseline. Although some non-target lesions may actually

be measurable, they need not be measured and, instead, should be assessed only qualitatively at the timepoints specified in the protocol.

- CR: disappearance of all non-target lesions
 - All lymph nodes must be non-pathologic in appearance
- Non-CR/Non-PD: persistence of one or more non-target lesion(s)
- PD: unequivocal progression of existing non-target lesions. For pathologic axillary lymph nodes, this may be based on a combination of morphological factors, including a potential increase in short-axis dimension

Special Notes on Assessment of Progression of Non-Target Disease

To achieve unequivocal progression on the basis of the non-target disease, there must be an overall level of substantial worsening in non-target disease in a magnitude that, even in the presence of SD or PR in target disease, the overall tumor burden has increased sufficiently to merit discontinuation of therapy. A modest increase in the size of one or more non-target lesions is usually not sufficient to qualify for unequivocal progression status. The designation of overall progression solely on the basis of change in non-target disease in the face of SD or PR of target disease will therefore be extremely rare.

New Lesions

The appearance of new malignant lesions denotes disease progression; therefore, some comments on detection of new lesions are important. There are no specific criteria for the identification of new radiographic lesions; however, the finding of a new lesion should be unequivocal, that is, not attributable to differences in scanning technique, change in imaging modality, or findings thought to represent something other than tumor. This is particularly important when the patient’s baseline lesions show partial or complete response. For example, necrosis of a breast lesion may be reported on an MRI scan report as a “new” cystic lesion, which it is not. A lesion identified during the study in an anatomical location that was not scanned at baseline is considered a new lesion and will indicate disease progression.

If a new lesion is equivocal, for example because of its small size, continued therapy and follow-up evaluation will clarify if it represents truly new disease. If repeat scans confirm there is definitely a new lesion, then progression should be declared using the date of the initial scan.

Time point Response (Overall Response)

Table 1 provides a summary of the overall response status calculation at each protocol-specified time point for which a response assessment occurs.

**Table 1 Time point Response: Patients with Target Lesions
 (with or without Non-Target Lesions)**

Target Lesions	Non-Target Lesions	New Lesions	Overall Response
CR	CR, or no non-target lesions identified at baseline	No	CR
CR	Non-CR/non-PD	No	PR
CR	NE	No	PR
PR	Any except PD	No	PR
SD	Any except PD	No	SD
NE (Any lesion)	Any except PD	No	NE
PD	Any	Yes or no	PD
Any	PD	Yes or no	PD
Any	Any	Yes	PD

CR=complete response; NE=not evaluable; PD=progressive disease;
 PR=partial response; SD=stable disease.

Missing Assessments and Not-Evaluable Designation

When no imaging/measurement is done at all at a particular time point, the patient is not evaluable at that time point. If only a subset of lesion measurements are made at an assessment, usually the case is also considered not evaluable at that time point, unless a convincing argument can be made that the contribution of the individual missing lesion(s) would not change the assigned time point response. Similarly, if one or more non-target lesions are not assessed, the response for non-target lesions should be “not evaluable” except where there is clear progression in non-target lesions that are assessed.

Special Notes on Response Assessment

Patients with a global deterioration of health status requiring discontinuation of treatment without objective evidence of disease progression at that time should be reported as “symptomatic deterioration.” Every effort should be made to document objective progression even after discontinuation of treatment. Symptomatic deterioration is not a descriptor of an objective response; it is a reason for stopping study therapy. The objective response status of such patients is to be determined by evaluation of target and non-target disease as shown in Table 1.
